There will be a total of 4 testing visits (visits 1, 2 3 and 4 as described above) prior to starting the study, after which, subjects will receive treatment for visits 5-16). After completion of treatment, the subjects will then be re-tested on the baseline assessments and resting state MRI (Post-intervention Visits 17, 18, 19 and 20the total amount of visits for TBI subjects will be 20.). Healthy Control Subjects will have a total of three testing visits (1-3) only.

The subjects with TBI will then be randomly assigned to one of two groups, each consisting of 10 subjects. Subjects will be randomized by a simple randomization method. They will have a 50/50 chance of being in either group by flipping of a coin. Randomization will be carried out by the PI. Subjects and study personnel performing assessments and data analysis will be blind to group assignment. Only the PI will be unblinded.

The experimental group will receive active tDCS for 20 minutes and computerized cognitive training twice a week for 30-45 minutes for 6 weeks as described below. The control group will receive sham-tDCS 20 minutes and computerized cognitive training for 30-45 minutes twice a week for 6 weeks (12 training sessions). The sham group will not receive real tDCS after completion of the study.

In addition, we will conduct a qualitative interview with each of the subjects. Giorgi's phenomenology (Giorgi 1985; Kleiman 2004) is the method that will be used to describe the experiences of persons undergoing tDCS for treatment of TBI. In-person audio-taped interviews will be conducted at the completion visit by an experienced qualitative interviewer and immediately transcribed verbatim. Interviews are expected to range from 30 minutes to 1 hour. Each of the subjects will be asked the open-ended question, "Please tell me about your experience undergoing tDCS for the treatment of traumatic brain injury." Probes included the following questions: "What was the experience like for you? What should we continue to do and what should we change to make the experience better for patients?" Themes will be derived using the constant comparative method (Sandelowski 1995; Thorne 2000).

II. CHARACTERSTICS OF THE RESEARCH POPULATION

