1. Number of Subjects. Forty (40) patients with complaints of emotional dysfunction 6 months post-brain injury between 18 and 85 years of age, and twenty-five (25) healthy control subjects will participate. The patients will be referred after discharge from the inpatient brain injury units of Bellevue Hospital and Hospital for Joint Diseases and from their outpatient TBI clinics, and will meet the inclusion-exclusion criteria listed below.

- 2. Gender of Subjects.** Both male and female subjects will be included. We will attempt to recruit 50% of male and 50% female subjects. There will be no gender based enrollment restrictions.
- 3. Age of Subjects.** The age range of subjects is between 18 and 85 years. The goal of this study is to understand emotional dysfunction in adult patients. Individuals below the age of 18 will be excluded from this study since pediatric TBI is relatively rare and the mechanisms of recovery may differ. Adults over 85 will be excluded to rule out possible confound of co-morbid medical conditions.
- 4. Racial and Ethnic Origin.** There are no exclusions based on gender or ethnic group.
- 5. Inclusion Criteria.**
 - (1) Brain Injury at least 6 months prior.
 - (2) Family or self-identification of cognitive or emotional difficulties.
 - (3) Unchanged and stabilized medical treatment in the three weeks prior to the screening.
- 6. Exclusion Criteria.**
 - (1) Any social or medical problem that precludes completion of the protocol.
 - (2) Presence of focal motor deficits in the upper extremities.
 - (3) Comorbid psychiatric disease such as schizophrenia, or active substance abusers (except nicotine).
 - (4) History of craniectomy, active infection, or seizure activity beyond 1 week post-TBI.
 - (5) Complicating medical problems such as uncontrolled hypertension, diabetes with signs of neuropathy, and previous neurological illness such as head trauma, prior stroke, epilepsy or demyelinating disease, implanted neuromodulatory or electronic device, metal in head
 - (6) Pregnancy

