- 7. Vulnerable Subjects.** Although TBI patients have some cognitive impairment, we will only consent patients who have been determined to have the capacity to give consent. This determination will be made by [name], [name] Im or [name] who are specialists in Brain Injury and will screen patients to determine if they are in a stable cognitive state, whose capacity to give consent is not expected to fluctuate. Only such patients will be enrolled in the study. We will provide information to the subjects in terms that they can fully understand, and capacity to consent will be determined by the subject's verbal understanding of the protocol as determined by the PI. We will not exert any overt or covert coercion, and no financial incentive will be offered. The consent document that each potential subject will be asked to sign will be written in the language that he or she understands, and will be approved by the IRB.

III. METHODS AND PROCEDURES

1. Methods and Procedures.

Patients will sign informed consent and be required to undergo self-assessment (using the TIRR symptom checklist), caregiver assessment (using the Neurobehavioral Functioning Inventory/NFI), and clinician assessment (using NRS-R) to determine neurobehavioral status on study entry. Screening procedures will also include medical history and interview, review of medications and imaging records to ensure that participants meet inclusion/exclusion criteria. Screening procedures will take place at the Motor Recovery Laboratory. The following outcome measures will be administered at baseline and at the end of the 6-week tDCS intervention.

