Auditory Consonant Trigrams (Peterson and Peterson 1959) is a test of information processing and divided attention. Three consonants are presented to the individual, who must remember them after intervals of 0, 9, 18 and 36 seconds. During intervals, the person is required to count backwards aloud by threes from different starting points. The task captures everyday experience of momentary distraction and subsequent loss of recently learned information and can identify dysfunction following mild neurological changes (Boone 1999).

Executive Function:

Stroop Color-Word Test (Golden 1978) is a measure of selective attention, verbal processing speed, cognitive flexibility and response inhibition. Poor performance on the Stroop has been found to be associated with frontal systems dysfunction secondary to closed head injury (Trenerry, Crosson et al. 1989). The test is a good discriminator between individuals with TBI and controls (Asikainen, Nybo et al. 1999; Bate, Mathias et al. 2001; Wallesch, Curio et al. 2001).

Trails B (Reitan and Wolfson 1985) is a speeded test of attention, sequencing, mental flexibility, visual search and psychomotor speed. The participant draws lines connecting alternating circles with numbers and letters in sequence. Speed of performance on Trails B is considered to be vulnerable to the subtle cognitive effects of TBI (Lezak 1995; Rasmusson, Carson et al. 1996). Test-retest reliability over two weeks was reported as .44 in a non-disabled sample and .67 in people with disabilities. Trails B errors are considered valid measures of dorsolateral prefrontal dysfunction (Stuss and Levine 2002).

Information Processing Speed:

Symbol Digit Modalities Test (Smith 1993) is used to measure visual scanning, tracking and motor speed, and it is sensitive to subtle cognitive impairment. A score below 1.5 standard deviations below the mean is indicative of cerebral dysfunction. Performance declines are observed with increasing age, demonstrating that cognitive changes could be detected with this measure. This test is sensitive to brain injury (Lezak 1995; Spreen and Strauss 1998).

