We will focus our investigations on the left DLPFC, as modulation of this area by tDCS has been shown to enhance working memory (Fregni, Boggio et al. 2005) which also demands similar attentional resources as emotional control (Anderson and Knight 2010). A constant current of 2 mA intensity will be applied for 20 min. Patients will feel the current as an itching sensation at both electrodes at the beginning of the stimulation. For sham stimulation, the electrodes will be placed in the same position; however, the stimulator will be turned off after 5 seconds (Siebner, Lang et al. 2004) so that patients will feel the initial itching sensation in the beginning, but receive no current for the rest of the stimulation period; this procedure has

been used to blind patients to the stimulation condition (Nitsche, Liebetanz et al. 2003; Nitsche, Schauenburg et al. 2003).

2. Data Analysis and Data Monitoring.

Power Analysis: This is a pilot feasibility study hence sample size is small and arbitrary. Power analysis from these pilot data will be used to determine sample size in future studies. Subjects with TBI will be randomized to the 2 treatment groups n=10 in each group.

Data Analysis:

1) To examine the relationship between alerting, orienting and executive attention and emotional recognition, reactivity and regulation in patients with TBI and controls.

Hypothesis: Patients with TBI will show clear patterns of attentional and emotional impairment compared with controls. Deficits in executive attention will be related to deficits in emotional appraisal in patients.

Scoring of emotional recognition, reactivity and regulation:

- 1) **Emotional reactivity film clips:** Physiological responses (cardiac inter-beat, finger pulse amplitude, finger pulse transmission time, ear pulse transmission time, and respiration period) will be recorded, and input from baseline will be subtracted from input across the most intense segment of the clip. Data will be combined into a single aggregate score for each diagnostic group to increase reliability and reduce noise; aggregate scores of patients and controls will then be compared. Facial behavior will be recorded and coded for displays of the target emotion across the most intense segment of the clip; data from patients and controls will then be compared.

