- 2) **Emotional recognition:** Responses to emotion recognition questions, using both the reactivity film clips described above and picture stimuli will be recorded and coded; coded data from patients and controls will be compared.
- 3) **Emotional regulation with disgust videos:** For the three conditions, physiological responses (as described above) will be recorded, and input from baseline will be subtracted from input across the most intense segment of the clip. Facial behavior will be recorded and coded. Data from patients and controls will be compared.

For coding facial behavior, coders will be blind to the diagnostic status of the participant and code videos with sound muted; coding will be assessed for inter-rater reliability

Pearson's correlation analysis will be performed to examine the relationship between reaction time (RT) scores indicating alerting, orienting and executive attention on the ANT-R and emotional recognition, reactivity and regulation scores. Differences in patients and controls will be computed. We will also correlate the clinical scores on the MARS with the ANT-R and the TAS-20 scores with the emotional battery scores. We expect that deficits in selective or executive attention will be related to deficits in emotional appraisal in the patients.

2) To determine whether anodal tDCS applied over the dorsolateral prefrontal cortex in conjunction with computer assisted cognitive re-training of attention will lead to greater improvement in attention and/or emotional regulation compared with sham-tDCS + cognitive re-training. Hypothesis: Patients receiving tDCS + cognitive re-training will show greater improvement in post-intervention measures of attention and emotional regulation.

A 2 (condition) x 2 (pre and post session) repeated measures ANOVA with a priori orthogonal contrasts will be performed on the variables related to executive attention and emotional appraisal to determine whether there is a difference both within and between groups. This analysis will also provide data for power analysis to determine the sample size for subsequent interventional studies. We expect that patients receiving tDCS + cognitive re-training will show greater improvement in post-intervention measures of attention and emotional regulation.

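### Aim 2's 2 x 2 pre/post ANOVA is a valid change-score test, but adjusting for the baseline already collected would usually give a more precise active-versus-sham estimate

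*Protocol*

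**What the plan says.** The Aim 2 analysis is fixed in Protocol section III.2 (Data Analysis, item 2): "A 2 (condition) x 2 (pre and post session) repeated measures ANOVA with a priori orthogonal contrasts will be performed". It covers the executive-attention and emotional-appraisal outcomes and is meant to show changes inside each arm as well as contrasts between the arms. The hypothesis there is "Patients receiving tDCS + cognitive re-training will show greater improvement in post-intervention measures of attention and emotional regulation". A contrast in improvement between arms is the condition-by-session interaction, although the text does not name that term. The baseline score is nowhere named as a covariate. The same paragraph says the analysis will feed the sample size of later trials.

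The baseline values exist. Section III.1 (Methods and Procedures) says: "The following outcome measures will be administered at baseline and at the end of the 6-week tDCS intervention".

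On allocation, section I.3 (Study Design) says "Subjects will be randomized by a simple randomization method", by coin flip and with no stratification. On size, section III.2 says "Subjects with TBI will be randomized to the 2 treatment groups n=10 in each group".

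On how closely two measurements agree, section III.1.1 says of Trails B: "Test-retest reliability over two weeks was reported as .44 in a non-disabled sample and .67 in people with disabilities". Section III.1.2 gives .77 for the TAS-20, and section III.1.3 gives .93 for the quality-of-life questionnaire. No retest value is given for the ANT-R or the film and picture battery.

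**The concern.** A change score subtracts the whole baseline value, as if each unit of baseline predicted exactly one unit of follow-up. When the pre/post correlation is clearly below 1, that over-corrects. In very small arms allocated by an unstratified coin flip, the baseline means will often differ by chance. The arm that starts worse then tends to look as if it improved more, through regression to the mean.

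What is at stake is the precision of the active-versus-sham estimate, in a pilot whose stated product is planning information for later trials.

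**Working it through.** **Reproduction.** The protocol gives no power, effect size, SD or alpha for Aim 2, so there is no figure of its own to reproduce.

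**Inputs from the protocol.** n = 10 per arm (section III.2); two measurement times; retest values .44 and .67 (Trails B), .77 (TAS-20) and .93 (quality of life).

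**Assumptions.** The retest values stand in for the pre/post correlation rho; pre and post SDs are equal (set to 1); arms are equal in size; the true effect is 0.8 SD; tests are two-sided at 5%.

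**Step 1, identity.** On one simulated data set with 10 per arm, the interaction F was 1.5802 and the squared t on change scores was 1.5802 (p = 0.2248 for both). The two tests are the same.

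**Step 2, variances of the treatment contrast.**
- Change score: 2(1 - rho) x 2/n.
- ANCOVA: (1 - rho²) x 2/n x (1 + 1/(2n - 4)). The last factor is the cost of estimating the slope.
- Ratio, ANCOVA to change: (1 + rho)/2 x (1 + 1/(2n - 4)). At n = 10 the last factor is 1 + 1/16 = 1.0625.

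| rho | (1 + rho)/2 | Ratio, 10 per arm | Simulated power, change to ANCOVA |
|---|---|---|---|
| .44 (Trails B, non-disabled) | 0.720 | 0.77 | 36% to 45% |
| .67 (Trails B, people with disabilities) | 0.835 | 0.89 | 55% to 60% |
| .77 (TAS-20) | 0.885 | 0.94 | 71% to 73% |
| .93 (quality of life) | 0.965 | 1.03 | no gain |

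Power comes from 40,000 simulated trials per setting. At .67 and .77 the standard error falls by about 6% and 3% (square roots of 0.887 and 0.940 are 0.942 and 0.970).

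**Step 3, break-even.** The ratio equals 1 when rho = 2 x 16/17 - 1 = 0.88 at 10 per arm. Above that ANCOVA does not gain; at .93 it loses about 3%.

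**Step 4, where the loss comes from.** The SE of the chance difference in baseline means is sqrt(2/10) = 0.447 SD. Given an observed difference, the change-score estimate moves in the opposite direction by (1 - rho) times it. For a 1-SE difference that is 0.33 x 0.447 = 0.15 SD at .67 and 0.23 x 0.447 = 0.10 SD at .77 (0.56 x 0.447 = 0.25 SD at .44). In simulation the ANCOVA estimate moved by about zero.

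The identity 2(1 - rho) = (1 - rho²) + (1 - rho)² shows that this movement is the extra variance. At .67 it reads 0.66 = 0.551 + 0.109, and at .77 it reads 0.46 = 0.407 + 0.053. The second term is the imbalance term.

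**Step 5, validity.** Simulated type I error at 10 per arm was 5.0% and 5.1% for the change score at .67 and .77, and 5.0% for ANCOVA at both.

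**Step 6, other sample size.** Section II.1 plans for "Forty (40) patients with complaints of emotional dysfunction 6 months post-brain injury between 18 and 85 years of age". That conflict with 10 per group is a separate matter. At 20 per arm the ratios are 0.74, 0.86, 0.91 and 0.99 in the order of the table, so the direction holds.

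**The case against.** The best defence is that nothing here is invalid. The planned test keeps its 5% error rate and is unbiased over repeated randomisation. A reader might infer that baseline imbalance biases the tDCS effect; the calculations do not support that. The shift exists only conditional on the imbalance that happens to occur, and the ANOVA's standard error already allows for it. Nor may the shift be counted as a second harm beside the lost precision, since step 4 shows they are the same quantity. This part of the defence stands in full.

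A reader might also infer that the change score is noisier than ignoring baseline altogether. That needs rho below .5. Only the .44 figure gives it (2 x 0.56 = 1.12 against 1.00), and that figure is from a non-disabled sample, whereas Aim 2 randomises only patients with TBI. At .67 and .77 the change-score variance is 0.66 and 0.46, well below 1.00. The stronger claim is not supported.

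The correlations are borrowed. Trails B was retested over two weeks, while this trial has a six-week intervention between measurements. The best slope is rho times the ratio of post to pre SD, so unequal SDs would change the figures. This limits confidence in the size of the gain, but not in the algebra.

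The study is a pilot with an admittedly arbitrary sample size and no power target to miss, and the ANOVA directly serves the within-group question. Both are fair and lower the severity. They do not remove the point, because estimates for planning are what the pilot is meant to deliver.

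Finally, covariate adjustment is often settled in an analysis plan, which is not at hand here. But the protocol names a specific method, so this is a stated choice and not a gap.

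**Conclusion.** The point holds as an efficiency recommendation. The Aim 2 interaction test is a correct change-score test that is usually less precise than a baseline-adjusted comparison of the same data. With .67 and .77 as proxies, the planned contrast has about 13% and 6% more variance than ANCOVA at 10 per arm (1/0.887 and 1/0.940). At the non-disabled value of .44 the excess would be about 31% (1/0.765). The gain disappears above a correlation of about 0.88, and the cost of adjusting at .93 is about 3%.

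Confidence is high in the identity and the formulas and moderate in the magnitude, which rests on the proxy correlations, equal SDs and, for power, the assumed 0.8 SD effect. The plan is inefficient, not wrong, and the change is worth making because it is nearly free.

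**What to change.** In section III.2, item 2, make the active-versus-sham comparison for each Aim 2 outcome an ANCOVA: post-treatment score on arm, with the baseline score of the same measure as covariate. Report the adjusted difference with its 95% confidence interval. Use that difference and the residual variance when sizing later trials. In large samples the change-score variance exceeds the adjusted variance by a factor of 2/(1 + rho), which is 1.20 at .67 and 1.13 at .77, so the choice carries through to the next sample size. Keep the 2 x 2 ANOVA and the within-group contrasts as descriptive results.

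The cost is a sentence or two of text and one error degree of freedom (17 instead of 18 at 10 per arm). No new data are needed.

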Relationship between attention and emotional function after traumatic brain injury (TBI): probing neural circuitry with transcranial direct current stimulation (tDCS)

I. PURPOSE OF THE STUDY AND BACKGROUND

1. Purpose of the study

The purpose of this pilot study is to investigate the relationship between attention and emotional function post-TBI in an effort to better understand the cognitive mechanisms of emotional processing in patients with TBI, and explore novel treatment strategies to improve emotional regulation using tDCS to modulate activity in the dysfunctional prefrontal-limbic circuits. This project will provide pilot data for extramural funding to expand on this topic.

The specific aims are:

1) To examine the relationship between alerting, orienting and executive attention and emotional recognition, reactivity and regulation in patients with TBI and controls.

Hypothesis: Patients with TBI will show clear patterns of attentional and emotional impairment compared with controls. Deficits in executive attention will be related to deficits in emotional appraisal in patients.

2) To determine whether anodal tDCS applied over the dorsolateral prefrontal cortex in conjunction with computer assisted cognitive re-training of attention will lead to greater improvement in attention and/or emotional regulation compared with sham-tDCS + cognitive re-training. Hypothesis: Patients receiving tDCS + cognitive re-training will show greater improvement in post-intervention measures of attention and emotional regulation.

3) To determine whether resting-state activation patterns in the fronto-limbic connections of patients receiving tDCS + cognitive re-training show greater improvement compared with sham-tDCS + cognitive re-training, using functional connectivity MRI (fMRI).

Hypothesis: Patients receiving tDCS + cognitive re-training will show higher temporal correlation between the frontal and limbic areas compared to baseline than patients receiving sham tDCS + cognitive re-training.

2. Background and Significance

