Accurate interpretation of emotion in oneself and others is critical for the successful negotiation of social interactions. Several studies have found that a significant proportion of individuals with TBI are unable to recognize and understand affective information from the face, voice, bodily movement, and posture of others, suggesting that they are impaired in emotional appraisal (Bornhofen and McDonald 2008; McDonald, Bornhofen et al. 2009). Lack of response to emotional stimuli is more prevalent for negative emotions, which may further accentuate the impact of the emotional processing deficit in social situations and contribute significantly to the behavioral dysfunction (Saunders, McDonald et al. 2006). In fact, difficulty identifying emotions has been associated with poorer quality of life, even when depression and anxiety are controlled for, and has also been uniquely associated with executive function deficits (Henry, Phillips et al. 2006).

It has also been suggested that the inability to recognize emotions may be related to deficits in error processing during sustained attention to response tasks (O'Keeffe, Dockree et al. 2004), even when controlled for severity of injury (McAvinue, O'Keeffe et al. 2005). Error feedback has been shown to lead to improvement in emotional recognition (McAvinue, O'Keeffe et al. 2005), but training in focused attention and mimicry have not (McDonald, Bornhofen et al. 2009). One recent study in a group of healthy volunteers found that individuals who had difficulty understanding, processing, or describing emotions (alexithymics) on the Toronto Alexithymia Scale (TAS-20) showed less efficient voluntary control of executive attention (Gu, Liu et al. 2008). Elucidating the relationships between specific aspects of attention and emotional processing inform the development of more effective, clinically translatable treatment strategies for behavioral dysfunction post-TBI.

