A primary goal of cognitive therapy is to enable the patient to more accurately assess a situation, using cognitive strategies such as emotional reappraisal, selective attention and reframing (Gross 1998; Gross and John 1998), in order to regulate the associated emotional responses (Allen, McHugh et al. 2008). In turn, successful treatment of emotional dysregulation (altering the emotional response) after TBI involves the employment of cognitive strategies that require the patient's active engagement and cognitive reappraisal of the event (Olsson and Ochsner 2008; Macnamara, Ochsner et al. 2010). Functional neuroimaging studies on reappraisal of negative affect have consistently reported increased activation of the DLPFC and/or VLPFC and decreased amygdala activation (Wager, Davidson et al. 2008; Ochsner, Hughes et al. 2009; McRae, Hughes et al. 2010). The cognitive regulation of emotion model (Ochsner, Bunge et al. 2002; Delgado, Nearing et al. 2008; Schiller and Delgado 2010) proposes that the DLPFC is involved in the effortful manipulation or interpretation of the emotional stimulus and the VLPFC may have a function in the selection of emotional interpretation (Wager, Davidson et al. 2008). The changes observed in the amygdala are thought to result from top-down modulation of the emotional meaning of the stimulus.

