1.2 Emotional Function Testing

Toronto Alexithymia Scale (TAS): Alexithymia refers to the condition of having trouble identifying and describing emotions, and minimizing emotional experience while focusing attention externally. The TAS is a well-validated and commonly used 20-item instrument to measure alexithymia. It is a self-reported scale with 3 subscales: describing emotions, identifying emotions, and externally-oriented thinking; each item is rated using a 5-point Likert scale whereby 1 = strongly disagree and 5 = strongly agree. The total alexithymia score is the sum of responses to all 20 items, while the score for each subscale factor is the sum of the responses to that subscale: equal to or less than 51 indicates non-alexithymia, equal to or greater than 61 indicates alexithymia. Scores of 52 to 60 indicate possible alexithymia. The scale demonstrates good internal consistency (Cronbach's alpha = .81) and test-retest reliability (.77, p<.01). Research using the TAS-20 demonstrates adequate levels of convergent and concurrent validity. The 3 factor structure was found to be theoretically congruent with the alexithymia construct. In addition, it has been found to be stable and replicable across clinical and nonclinical populations (Bagby, Parker et al. 1994; Bagby, Taylor et al. 1994).

Emotional Function Battery

For a comprehensive objective measurement of emotional function, we will employ paradigms from basic affective science to comprehensively assess multiple aspects of emotional function, including emotional recognition, reactivity, and regulation in an ecologically valid manner using film clips (Werner, Roberts et al. 2007; Goodkind, Gyurak et al. 2010).

a. Emotional Reactivity: Patients will view a series of short (~3 min.) film clips that have been selected for their ability to produce particular positive and negative emotions (Gross and Levenson 1993; Gross 2007). During each film, physiological responses will be measured and facial behavior will be coded. Following each film clip patients will be asked to provide subjective ratings of the nature and intensity of their emotional responses to the film clips. **Film clips intended to induce happiness, sadness, fear, and neutral emotion will be used.**

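### Aim 2 hypothesises an effect on emotional regulation, but its only arm comparison is on emotional appraisal, which is not a scored construct and on one reading leaves regulation untested

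*Protocol*

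**What the plan says.** Specific aim 2 (section I.1) asks whether active stimulation leads to "greater improvement in attention and/or emotional regulation compared with sham-tDCS + cognitive re-training". Section III.2, Data Analysis, item 2 repeats that aim. It gives the hypothesis that patients on active stimulation "will show greater improvement in post-intervention measures of attention and emotional regulation", and closes by expecting the same result.

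Between hypothesis and expected result stands the only test of Aim 2: a repeated measures ANOVA, condition by pre/post session, on "variables related to executive attention and emotional appraisal to determine whether there is a difference both within and between groups". The same item says this analysis will supply data for sizing later interventional studies.

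Section III.1.2 describes the emotional battery as "including emotional recognition, reactivity, and regulation in an ecologically valid manner using film clips". The scoring rules in section III.2 use the same three headings. The alexithymia scale has subscales for describing emotions, identifying emotions and externally oriented thinking.

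**The concern.** The constructs change in the test sentence and change back in the next statement of the expected result. Emotional regulation becomes emotional appraisal, and attention becomes executive attention. Because no instrument or scoring rule produces a score called appraisal, the reader must decide what the emotional half of the test is.

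Two things are at stake. An analyst could follow the sentence faithfully, test recognition, and leave the regulation hypothesis without any comparison of arms. Or the choice among fitting scores could be made after the data are seen. In either case the outcome and effect size obtained would carry into the planning of later studies, which is a stated purpose of this pilot.

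**Working it through.** **1. What appraisal could mean, from the protocol's own uses.**

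- *Recognition.* Background 2.1 reports that patients fail to recognise and understand the affect of others, "suggesting that they are impaired in emotional appraisal". On this reading the ANOVA is on the recognition scores, and regulation is untested.
- *Regulation.* Background 2.3 describes cognitive therapy "using cognitive strategies such as emotional reappraisal, selective attention and reframing" "in order to regulate the associated emotional responses". This concerns reappraisal, a related word. On this reading regulation is tested.
- *Umbrella term.* The Aim 1 hypothesis is "Deficits in executive attention will be related to deficits in emotional appraisal in patients", and its analysis correlates the attention scores with all three emotional domains. On this reading regulation is tested along with the other two.

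Two of the three readings test the hypothesis and one does not. No sentence in the protocol chooses between them.

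**2. Attention.** Aim 1 uses the ANT-R alerting, orienting and executive scores; the Aim 2 test names only the executive part. By the protocol's descriptions in section III.1.1, four scores fit variables related to executive attention: the ANT-R executive score, MARS restlessness/distractibility (described as similar to it), Stroop (selective attention) and Auditory Consonant Trigrams (divided attention).

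**3. Room for selection (illustration).** Physiology is counted as one score per condition.

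- Recognition reading: 4 attention + 2 recognition (film clips, pictures) = 6.
- Regulation reading: 4 attention + 6 regulation (suppress clip, amplify clip and anticipated startle, each for physiology and behaviour) = 10.

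The chance of at least one p<.05 with no treatment effect, if the scores are independent, is 1 − .95^k:

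- k = 6: 1 − .95^6 = .265
- k = 10: 1 − .95^10 = .401

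Simulation (40,000 runs, 10 per arm, equal correlation .5 between scores, two-sided t-test at .05) gives .213 and .300. The two-sided .05 level and the correlation are assumptions; the protocol states neither for Aim 2.

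**4. ANCOVA against the planned group-by-time test.** The group-by-time test is equivalent to comparing change scores. With n per arm and pre-post correlation r,

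Var(ANCOVA) / Var(change) = (1 + r)/2 × [1 + 1/(2n − 4)].

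The bracket is 1.0625 at n = 10 (the stated group size) and 1.0278 at n = 20 (half of the 40 patients also stated). The values of r are the retest coefficients that the protocol quotes for other instruments.

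| r | Source | n = 10 | n = 20 |
|---|---|---|---|
| .67 | Trails B, people with disabilities | .887 | .858 |
| .77 | alexithymia scale | .940 | .910 |
| .93 | quality-of-life questionnaire | 1.025 | .992 |

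Break-even is at r = 2/1.0625 − 1 = .88 for n = 10, and 2/1.0278 − 1 = .95 for n = 20.

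**The case against.** The sentences on either side of the ANOVA both name emotional regulation, and Aim 1 uses appraisal as a summary of all three domains. A sympathetic reader would therefore take regulation to be included. That reading is available and may be the intended one. It does not remove the problem, because the Background supports the recognition reading just as directly.

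Executive attention is a legitimate component of attention, the aim itself says and/or, and the Aim 1 hypothesis also concerns executive attention. This stands: testing only the executive part is not an error. The remaining fault is that the hypothesis is worded more broadly than the test.

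The list of scores for a named construct is commonly left to a statistical analysis plan. This also stands, and it is why the selection figures are an illustration only. The change of construct is different: an analysis plan that followed the protocol faithfully would inherit it.

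Three stronger inferences are tempting and not supported:

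- *That regulation is definitely untested.* Two of the three readings test it.
- *That all fitting scores can be pooled into one larger count.* The recognition and regulation readings are alternatives, so their scores should not be added. The counts of 6 and 10 are themselves judgements: Trails B, listed under executive function, and subjective responses are left out, and the protocol gives no scoring rule for startle.
- *That the repeated measures ANOVA is wrong.* Its group-by-time test is valid under randomisation.

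**Conclusion.** The point holds as an inconsistency in the stated rule. The Aim 2 hypothesis and its only arm comparison name different constructs, and the one tested is not scored. Whether regulation is tested depends on a reading that the protocol does not fix.

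The scope for choosing among scores is moderate: 27% or 40% if independent, about 21% or 30% at correlation .5. It rests on the counts and assumptions above and says nothing about how the analyst will behave.

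The ANCOVA gain is secondary. At 10 per arm it is about 11% lower variance at r = .67 and 6% lower at .77, with a cost of about 3% at .93. The protocol gives no pre-post correlation for the ANT-R or the film scores, so the size of any gain for the actual outcomes is unknown. The correction should be made; it does not call the design into question.

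**What to change.** In section III.2, Data Analysis, item 2:

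- In the ANOVA sentence, replace emotional appraisal with emotional regulation. Name the scores that the scoring rules already define: baseline-subtracted physiology and coded facial behaviour for the disgust clips under the suppress and amplify instructions, with the no-regulation clip as reference. If recognition is also meant, list it by name and add it to the hypothesis.
- For attention, either name the ANT-R executive score and narrow the hypothesis to executive attention, or test all three ANT-R scores.
- Report every named score. This removes selective choice, though not multiplicity. With 4 regulation scores and 1 or 3 attention scores, the chance of at least one p<.05 under the null is still 1 − .95^5 = 23% or 1 − .95^7 = 30% if independent, so the results should be read as pilot estimates.
- Difference indices between instructions, and a startle score, are optional; the protocol would have to define them first.
- As an inexpensive improvement, estimate the arm effect by ANCOVA of the post score on arm with the baseline score as covariate, and keep within-group changes descriptive.

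The cost is wording. Section III.1 already has the outcome measures taken at baseline and at the end of the 6-week intervention, so no visit or assessment is added. ANCOVA uses one degree of freedom and loses a little precision only if the pre-post correlation exceeds about .88 at 10 per arm.
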